Several types of substances do not present an inherent irritant or allergenic potential, however, they may provoke skin reactions when exposed to sunlight, either because ultraviolet radiation converts them into other substances, or because they are photo activated to excited states capable of interacting with the skin. (Billhimer, 1990). Specifically, topically applied agents can cause contact dermatitis or interact with sunlight to cause phototoxic reactions. These reactions occur on first exposure to the

 GlaxoSmithKline	Document Name	Clinical Protocol 207587		
	Type	Version	Document Identifier	Effective Date
	eldo_clinical_doc	2.0; Most-Recent; Effective; CURRENT	090032d580d16e68	24-Mar-2017 07:31:59
	Reason For Issue	Auto Issue		

product and usually resemble exaggerated sunburn and may be characterised by a sensation of prickling and burning.

Among the several types of safety assays in humans, patch tests are currently the most widespread protocols conducted in order to investigate the potential risk for possible irritation and/or sensitization agents that, when in contact with the human skin, may trigger a reaction.

Skin sensitisation is an immunological process in which the responsiveness to a specific chemical allergen is increased. By definition, skin sensitisation is induced when a susceptible individual is exposed to an inductive chemical allergen. This allergen causes a skin immune response that, at a certain range, will result in the development of contact sensitisation (Kimber *et al.*).

The phototoxicity test measures the potential of a test product to produce phototoxic reactions in human subjects upon exaggerated application. Evaluator comparison of cutaneous responses to test product alone, test product exposed to UVA radiation and an irradiated, control product site provides an assessment of the phototoxic potential of the test product.

Topically applied products may contain one or more ingredients that can be converted to a photoantigen by UVA radiation. In certain individuals, the photoantigen can then trigger an inflammatory response by the immune system and produce an allergic reaction upon subsequent exposure to the product in sunlight.

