The photoallergenicity test measures the potential of test products to produce allergic reactions in the presence of UVA radiation. This test consists of three phases: a 3-week Induction phase consisting of repeated 24 hour semi-occlusive patch applications on the backs of healthy subject and subsequent exposure to UVA radiation after each patch removal; a 2 week Rest phase; and a final Challenge phase, consisting of two parallel 24 hour semi-occlusive patch applications to naive sites, one of which is subsequently exposed to UVA radiation upon patch removal, and evaluation of cutaneous responses of both sites 24, 48 and 72 hours after patch removal.

The inclusion of evaluations at 24, 48 and 72 hours for the two challenge sites (with and without exposure to UVA radiation) provides simultaneous evaluation of the potential for contact irritation, phototoxicity, contact allergy and photoallergy.

 GlaxoSmithKline	Document Name	Clinical Protocol 207587		
	Type	Version	Document Identifier	Effective Date
	eldo_clinical_doc	2.0; Most-Recent; Effective; CURRENT	090032d580d16e68	24-Mar-2017 07:31:59
	Reason For Issue	Auto Issue		

The objective of this clinical study is to assess the phototoxicity and photosensitisation potential of a cosmetic test product under exaggerated conditions of use with controlled product application and under supervision of a dermatologist.

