2. OBJECTIVE(S) AND ENDPOINT(S)

Objective(s)	Endpoint(s)
Primary	
To determine the photoirritation and photosensitisation potential of a cosmetic facial skin product after repeated patch applications to the skin of healthy subjects.	Trained assessor assessment of local tolerance through visual assessment of cutaneous irritation via the combined dermal response and other effects scores over the induction and challenge phase.
Secondary	
To evaluate the tolerance of a cosmetic facial skin product.	Assessment of frequency and severity of Adverse Events

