3. STUDY PLAN

3.1. Study Design

Overall Design
This is an assessor-blinded (single), test site randomised, intra-subject comparison, repeated insult patch test to evaluate the skin irritation and sensitisation potential of a cosmetic facial product, under exaggerated conditions of use with controlled product application and under supervision of a dermatologist.
Day -14 to 0 / Visit 1 - Screening Visit
NOTE: Visit 1 and Visit 2 could be combined
The following assessments will be conducted: 
 1. Subject Informed Consent taken 2. Subject demographics collected 3. Medical history details 4. Details of current and concomitant medication collected 5. Fitzpatrick Skin Type Assessment (Appendix 3) 6. Inclusion/Exclusion criteria 7. Dermatologist determination for eligibility to participate in the study (including visual examination of the dorsum scapular region) 8. Subject eligibility
Days 1 to 22 / Visit 2 - Visit 14 - Induction Phase (3 Weeks)
NOTE: Visit 1 and Visit 2 could be combined

 GlaxoSmithKline	Document Name	Clinical Protocol 207587		
	Type	Version	Document Identifier	Effective Date
	eldo_clinical_doc	2.0; Most-Recent; Effective; CURRENT	090032d580d16e68	24-Mar-2017 07:31:59
	Reason For Issue	Auto Issue		

1. The following assessments will be conducted:
2. Continued eligibility check
3. Current/Concomitant Medications review
4. Inclusion/Exclusion criteria review (Inclusion criteria 3c (only) at Visit 2, if Visit 1 and 2 are not combined).
5. Dermatologist determination for continued eligibility to participate in the study (Visit 2/Day 1 only - if visits not combined)
6. Test Site Designation and Randomisation (Visit 2/Day 1 only)
7. Baseline grading/assessment of test sites (Per Appendix 2) (Visit 2/Day 1 only)
8. Patch applications (6 patch applications every Monday and Thursday, for 3 consecutive weeks).
9. Patch removal 24 (\pm 2) hours after application (Tuesday and Friday). Reaction grading/assessment performed by a qualified staff member (24 \pm 2 hours after application). Grading/assessments will be 30 minutes (up to 1 hour) after each patch removal (per Appendix 2)
10. Application site exposed to UVA irradiation.
11. **24 48** (\pm 2) hours after each UVA irradiation (or 72 (\pm 2) hours, in case of irradiation on Fridays), the sites will be evaluated for signs of dermatological reactions, according to Appendix 2.
12. Adverse event assessment

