Dermal irritation or sensitisation reactions within the patch area (i.e., irritation reactions outlined in Appendix 2) will not be recorded as AEs during the study. Reactions to the patch itself will also not be recorded as AEs. Unexpected reactions

 GlaxoSmithKline	Document Name	Clinical Protocol 207587		
	Type	Version	Document Identifier	Effective Date
	eldo_clinical_doc	2.0; Most-Recent; Effective; CURRENT	090032d580d16e68	24-Mar-2017 07:31:59
	Reason For Issue	Auto Issue		

(e.g., rash, hives) will be recorded as AEs. As each subject will be exposed to UVA radiation during the induction and challenge phases, it is expected that the sites become hyperpigmented and may exhibit erythema as a natural response to UVA exposure. These responses are expected and will be disregarded in evaluations, using the negative control (saline solution) as the standard for determining the expected degree of reaction.

Reactions observed after application of patches and before UVA exposure, or observed on the non-irradiated site during the challenge phase, will be used to evaluate the primary irritation potential of the product. These data will not be used to evaluate the photoirritation or photosensitisation potential of the formulation.

Application Amount Justification:

The prerequisite for a patch test is the requirement that the whole test site is covered with the test product, without spreading or overlapping into other test sites. Previous work (Isaksson, 2007) has shown that the optimal dose to fulfil these requirements is 0.02 ml/cm².

The test product will be distributed over the patch test filter paper discs (semi occlusive patch application) in the amount of 0.02 ml, and applied to designated sites on the back. A sodium chloride (NaCl) saline solution (0.9%) will be used as the negative control and will also be applied to the back through semi-occlusive application.

The semi-occlusive patches are made of a hypoallergenic material with round chambers (or cells) of an absorbent material. Standardized amounts will be applied in these cells, approximately 0.02 ml (if application with a pipette is possible) or 20 mg (if application with a pipette is not possible, in this study, only products of the sponsor, GlaxoSmithKline will be tested with the saline solution control. One of the patch cells will contain the control and therefore, will be filled in with saline solution, and one of the other cells will be filled with the test product.

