9.2.3. Criteria for Evaluation

The primary evaluation will be to assess the phototoxicity and photosensitisation potential of the test and control product, based on the irritation (dermal response) and superficial irritation (other effects) score/grade after patch removal during the induction and challenge phase using the ITT population.

Safety and tolerability will be evaluated by adverse events assessments using the Safety population.

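### Protocol 3.4 bars the non-irradiated Challenge readings from the photo-evaluation, which contradicts the Introduction and leaves reactions at both Challenge sites without a classification

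*Protocol*

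**What the plan says.** Protocol 3.4 (Patch Assessments) deals with two sets of readings together: those made after patching but before UVA, and those at the Challenge site that gets no UVA. Reactions "observed on the non-irradiated site during the challenge phase, will be used to evaluate the primary irritation potential of the product". The next sentence is: "These data will not be used to evaluate the photoirritation or photosensitisation potential of the formulation". Just before this, 3.4 says that pigmentation and erythema expected from UVA are to be disregarded, "using the negative control (saline solution) as the standard for determining the expected degree of reaction".

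The Introduction (Protocol section 1) describes a different use of the same readings. Phototoxic potential is assessed through "Evaluator comparison of cutaneous responses to test product alone, test product exposed to UVA radiation and an irradiated, control product site". Grading both Challenge sites at 24, 48 and 72 hours "provides simultaneous evaluation of the potential for contact irritation, phototoxicity, contact allergy and photoallergy".

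The primary objective in section 2 is "To determine the photoirritation and photosensitisation potential of a cosmetic facial skin product after repeated patch applications". Section 3.1 states the design aim more broadly, as a "repeated insult patch test to evaluate the skin irritation and sensitisation potential of a cosmetic facial product". Section 9.2.3 bases the primary evaluation on the "score/grade after patch removal during the induction and challenge phase using the ITT population" and does not separate the two Challenge sites. Section 9.2.2 excludes no data. The SAP (2.4.1.1 and the shells of Tables 14.2.1.1, 14.2.2.1 and 14.2.2.2) tabulates scores by product, phase and visit, with one column per product and no split by irradiation.

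**The concern.** Each Challenge patch holds both products and only one patch site is irradiated, so every subject supplies four cells: product and saline, each with and without UVA. A photo-effect is what light adds to the product's own effect, and the cell that shows the product's own effect is product without UVA. Section 3.4 takes that cell out of the photo-evaluation. It also takes out the Visit 16 reading made at the irradiated site before exposure.

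What remains is irradiated product against irradiated saline. That contrast removes plain UVA erythema. It does not remove a reaction to the product that needs no light.

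The single use given to the barred readings is also narrow. By Challenge a subject has had six Induction applications and a two-week rest. A reaction on naïve skin at that point may be contact allergy, which the Introduction says the two sites help to evaluate. Section 3.4 offers only primary irritation, and it also keeps sensitisation reactions within the patch area out of adverse event recording.

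At stake is the answer to the primary objective: whether a reaction seen under UVA is attributed to light or to the product alone.

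**Working it through.** The plan states no reaction rate, effect size or classification figure, so there is nothing to reproduce. The check compares the two texts on each possible outcome and then sizes one reclassified subject.

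**Step 1. Patterns for the test product at Challenge, with saline clear.**

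| Irradiated product site | Non-irradiated product site | Section 3.4 read literally | Comparison in the Introduction |
|---|---|---|---|
| no reaction | no reaction | none | none |
| reaction | no reaction | photo-reaction | photo-reaction |
| no reaction | reaction | primary irritation | contact irritation or contact allergy |
| reaction | reaction | photo-reaction plus primary irritation | contact irritation or contact allergy; no photo component shown by presence alone |

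The two texts lead to different labels in two of the four patterns. No pattern under 3.4 has a contact-allergy label.

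**Step 2. Why the remaining contrast fails for the last row.** Write T for product and S for saline, with subscript u for UVA and n for no UVA. Let the product react equally at both sites with score s > 0 and let saline be clear.

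- Contrast left by 3.4: T_u − S_u = s − 0 = s, which looks like a photo-effect.
- Contrast using all four cells: (T_u − T_n) − (S_u − S_n) = (s − s) − (0 − 0) = 0, which shows no photo-effect.

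**Step 3. Do the planned outputs recover the distinction?** The SAP shells have one column per product. At each post-removal Challenge visit a subject has two readings per product, one irradiated and one not, and the shells do not say how the two enter the count. SAP 2.4.1.2 and 2.4.1.3 (model and supportive analyses) are marked not applicable. The individual observations and narratives promised in Protocol 3.4 and 9.3.2 would show the scores at both sites but do not classify them.

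**Step 4. Size of one subject.** Inputs: at least 30 randomised and at least 25 evaluable (Protocol 9.1). The number k of both-site reactors is an assumption. Shift in an apparent photo-reaction frequency = k/n:

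| k | n = 30 | n = 25 |
|---|---|---|
| 1 | 1/30 = 3.3% | 1/25 = 4.0% |
| 2 | 2/30 = 6.7% | 2/25 = 8.0% |
| 3 | 3/30 = 10.0% | 3/25 = 12.0% |

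Exact (Clopper-Pearson) two-sided 95% limits show what one such subject does to an otherwise clean result. With n = 25, 0/25 (0 to 13.7%) becomes 1/25 (0.1 to 20.4%). With n = 30, 0/30 (0 to 11.6%) becomes 1/30 (0.1 to 17.2%).

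**The case against.** The best case for the plan has five parts.

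1. Section 3.4 may mean only that a reaction seen without UVA is not in itself evidence of a photo-effect. Pairing that site with pre-UVA readings fits this, and it would leave the Introduction's comparison available. The reading is possible, but the sentence bars use of the data outright, and even the narrow reading leaves both-site reactions unclassified.
2. A reader might infer that a both-site reactor will be counted as photo-reactive. The visible documents state no such rule. The saline sentence concerns expected UVA responses. Section 6.2.2 makes the trained examiner's interpretation final and has a dermatologist available for a same-day second assessment of positive reactions. Appendix 2 is redacted, so criteria there cannot be ruled out. This stands: the mislabelling follows from the literal text and is not a stated outcome.
3. A reader might also infer that contact allergy would go unreported, or be reported as nil. The documents do not support this. Every score above zero gets a narrative, individual observations are presented, and both Challenge sites are graded at Visits 17 to 19. The reaction would be visible. What is missing is an output that names it as a contact reaction.
4. The bar does not appear in Protocol section 9 or in the visible SAP text, and no photo-reaction rate is a planned output. This also stands, and it makes the percentages illustrative only. It does not settle the conflict, because the SAP states no rule of its own.
5. Contact allergy is not in the primary objective, and for that objective the error would overstate photo-hazard and not hide it. This is correct. The main loss is therefore the within-subject comparator for the photo-evaluation.

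**Conclusion.** The point holds as a contradiction between current passages with a consequence for the primary objective. Section 3.4 removes the light-independent readings of the product from the photo-evaluation, while the Introduction relies on them. Applied literally, 3.4 cannot distinguish a product reaction of equal strength with and without UVA from a photo-reaction, and no planned output classifies it as a contact (possibly allergic) reaction.

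Its size cannot be fixed from the documents. If a both-site reactor were read that way, each would add 3.3 points with 30 subjects or 4.0 with 25. This assumes literal application of 3.4, a clear saline cell, and no overriding rule in the redacted appendix. If such a rule exists, the conflict between 3.4 and the Introduction still needs resolving.

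**What to change.** **Protocol 3.4.** Reconcile the two sentences with the Introduction. State that non-irradiated Challenge-site readings are the within-subject comparator for the photo-evaluation as well as the basis for judging contact irritation and contact allergy.

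**SAP tables.** Split the Challenge columns of Tables 14.2.1.1, 14.2.2.1 and 14.2.2.2 by irradiation status.

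**SAP classification.** Add a cross-classification per subject from the four cells at Visits 17 to 19, based on the combined score, with these categories:

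- reaction at the irradiated product site only;
- reaction at both product sites;
- reaction at the non-irradiated product site only;
- saline reacting as much as product.

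Fix two things before unblinding: the score difference that counts as reacting more (including where both product sites react but the irradiated one is stronger), and the rule for combining the three visits. Report both-site and non-irradiated-only reactors as light-independent contact reactions (irritation or contact allergy), each with a narrative.

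**Cost.** Protocol and SAP wording, a derived variable and revised table shells. All the readings are already scheduled, so no visit, procedure or subject is added.

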During the induction phase, there will be 6 patch applications (a patch will contain both the test product and saline solution) over 3 consecutive weeks, with each patch applied on Mondays and Thursdays. Each patch will remain in place for 24 (\pm 2) hours and then be removed, the treated areas will be cleaned with saline solution. After 30 minutes (maximum of 1 hour) the sites will be graded/evaluated as per the scale in Appendix 2. The patch test site will then be exposed to 5 J/cm² UVA radiation. The patch application site will be assessed pre-irradiation, following patch removal. Irradiation time depends on the power output of the light source and distance from the subject, and will be determined by the study site prior to UVA exposure. Irradiation will occur on the same days as patch removal (Tuesday and Fridays). Assessment of the irradiated sites will occur 48 hours (or 72 hours if the irradiation occurred on a Friday) after UVA exposure, prior to new patch application to the same site.

Rest Phase:

After the last grading/evaluation of the Induction Phase, subjects will enter a Rest Phase of 2 weeks. During this time there will be no product patch applications.

Challenge Phase:

After completing the Rest Phase, subjects will return for the Challenge Phase. Two naïve sites (previously un-patched, virgin areas) will be selected for the challenge patches both of these naïve areas will be graded/evaluated prior to any product application. Two patches, each with the test product and saline solution, will be randomly applied to each of the Challenge sites for 24 (\pm 2) hours, according to each subject's random assignment on Day 1 of the Induction phase. After 24 (\pm 2) hours, subjects will return for Challenge patch removal, the sites will be cleaned with saline solution and then graded/evaluated after 30 minutes (maximum of 1 hour). One of the Challenge patch sites will then be irradiated with 5 J/cm² of UVA radiation. Subjects will return 24 (\pm 2), 48 (\pm 2), and 72 (\pm 2) hours after patch removal for further grading/assessments of both the irradiated and non-irradiated Challenge sites.

End of Study:

After the Challenge phase is complete, a final clinical assessment by a qualified dermatologist will be performed to ensure that it is medically appropriate to exit each subject from the study. After all study assessments are completed, subjects will be discharged from the study site.

 GlaxoSmithKline	Document Name	Clinical Protocol 207587		

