9.2.2. Exclusion of Data from Analysis

No data will be excluded from any analysis.

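### Pre-UVA Induction readings are assigned to primary irritation alone although five of six fall on already irradiated skin, and the SAP maxima pool them with post-UVA readings

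*Protocol*

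**What the plan says.** Protocol 3.4 (Patch Assessments) sends two kinds of reaction to the evaluation of primary irritation: "Reactions observed after application of patches and before UVA exposure, or observed on the non-irradiated site during the challenge phase". It then closes the other route: "These data will not be used to evaluate the photoirritation or photosensitisation potential of the formulation". The rule does not distinguish the first Induction cycle from later ones.

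The same section (Induction Phase) sets out the cycle. A patch is worn for 24 hours and removed, and the site is graded about 30 minutes later. On that grading it says "The patch application site will be assessed pre-irradiation, following patch removal". UVA at 5 J/cm² follows the same day. The irradiated site is read 48 hours later, or 72 hours after a Friday irradiation, "prior to new patch application to the same site". Protocol 3.4 and 6.2.2 allow one departure from this path: after a combined score of 3 or more in Induction, the site is not irradiated and the next patch goes to an adjacent naïve site.

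The analysis sections do not carry the rule. Protocol 9.2.3 and SAP 2.4.1.1 base the evaluation of photo-potential on scores after patch removal in both phases, with no split by UVA. SAP 2.4.1.1 tabulates scores by visit and adds one maximum per phase regardless of visit; Protocol 9.3.2 likewise takes a maximum over time points. The programming notes to SAP Tables 14.2.1.1 and 14.2.2.1 define Induction as Visits 2 to 13, and the first of them puts Visit 14 under Rest. SAP section 3 declares no change from the protocol.

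**The concern.** The rule in Protocol 3.4 works only if a reaction seen before that day's UVA cannot be due to UVA. That is true of the first cycle. From the second cycle on, the skin under the patch has already received product and UVA together, so a reaction at patch removal may come from the product alone, from the earlier irradiation of treated skin, or from both.

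Induction offers no way to separate these causes. There is no non-irradiated test-product site in that phase. The irradiated saline cell shows the erythema expected from UVA by itself, but it cannot distinguish product irritation from a product photo-reaction.

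The attribution of low-grade Induction reactions bears on the primary objective, photoirritation and photosensitisation potential. Under Protocol 3.4 such a reaction at patch removal is irritation only. Under Protocol 9.2.3 and SAP 2.4.1.1 it is part of the photo-evaluation. Two analysts could therefore classify the same score in opposite ways, each with a passage in support.

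**Working it through.** **Inputs.** Visit days come from the Schedule of Events. Patches are applied on Days 1, 4, 8, 11, 15 and 18. Removal, grading and UVA fall on Days 2, 5, 9, 12, 16 and 19. Post-UVA readings fall on Days 4, 8, 11, 15, 18 and 22. The dose is 5 J/cm² per irradiation (Protocol 3.4).

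**The plan's own count.** Protocol 3.4 states 11 post-baseline Induction assessments and one in the Rest Phase. Visits 3 to 13 give 11: six pre-UVA (Visits 3, 5, 7, 9, 11, 13) plus five post-UVA (Visits 4, 6, 8, 10, 12). Visit 14 is the sixth post-UVA reading. The figure is reproduced.

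**Earlier UVA at each pre-UVA reading, default path.** Earlier exposures = number of removals before this one; cumulative dose = 5 × that number; hours = 24 × days since the last irradiation.

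| Visit (day) | Earlier UVA exposures | Cumulative J/cm² | Hours since last UVA |
|---|---|---|---|
| 3 (2) | 0 | 0 | none |
| 5 (5) | 1 | 5 | 72 |
| 7 (9) | 2 | 10 | 96 |
| 9 (12) | 3 | 15 | 72 |
| 11 (16) | 4 | 20 | 96 |
| 13 (19) | 5 | 25 | 72 |

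Five of six readings (5/6 = 83%) are on previously irradiated skin. With complete data and no relocation, that is 5 × 25 = 125 of 6 × 25 = 150 test-product readings for 25 completers, or 5 × 30 = 150 of 6 × 30 = 180 for 30 subjects.

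**Relocation.** Suppose patch m (m = 2 to 6) is the first on the naïve site and patching then continues. The old site contributes m − 2 previously irradiated readings and the new site 6 − m. The total is (m − 2) + (6 − m) = 4 of 6, whatever m is.

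**Which reactions are exposed.**
- A reaction already visible at the 48 or 72 hour reading (Visits 4, 6, 8, 10, 12) is recorded there, where it remains eligible for the photo-evaluation. If it lasts to the next removal it appears under both headings and is not lost.
- After a Tuesday irradiation the post-UVA reading is at 48 hours. The 72 hour point falls on the Friday pre-UVA grading (Visits 5, 9, 13). A reaction first appearing between the two would count as irritation only, unless it lasted to the next post-UVA reading. The protocol regards 72 hours as informative: it is a planned reading of the irradiated Challenge site.
- After a Friday irradiation the 72 hour reading (Visits 6, 10, 14) is already photo-eligible, so this gap does not arise.
- A reaction that clears and recurs on re-application is likewise first seen at a reading assigned to irritation.

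**The pooled maximum.** Visits 2 to 13 are 12 readings: one baseline, six pre-UVA and five post-UVA. The sixth post-UVA reading, Visit 14, is left out, although SAP 1.1 itself labels Visits 2 to 14 as Induction and the protocol's schedule notes describe Visit 14 as the final reading of the Induction irradiation.

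**The case against.** The strongest reply is that the rule concerns reactions, not readings. A zero grade on previously irradiated skin is not misclassified, and neither is a true irritant reaction. A reader might infer from 83% that five readings in six are misclassified. The documents do not support that; the figure counts readings where confounding is possible. This part of the reply stands.

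Several other parts stand too. A continuously persisting reaction is caught at the post-UVA reading. Relocation at a combined score of 3 or more limits what is carried forward mostly to scores of 1 to 2, although a new reaction at a pre-UVA grading can still be higher. The first grading at a relocated site is itself UVA-naïve. Photosensitisation is tested mainly by the Challenge contrast of irradiated and non-irradiated naïve sites, which this rule leaves intact.

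A reader might also infer that photo-evidence is discarded or that an irritation result is inflated. Neither is shown. The SAP does not implement the rule, specifies no separate primary-irritation output, and tabulates scores by visit. Nor is there a firm conflict with Protocol 9.2.2, "No data will be excluded from any analysis": the rule assigns readings to a question of interpretation, and they are still graded, tabulated and described.

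Moving all these readings into the photo-evaluation would bring the opposite risk. Without a non-irradiated product site in Induction, cumulative irritation could be counted as a photo-reaction.

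It might finally be said that the rule means before any UVA at all, which would leave only Visit 3 within Induction on the default path. The protocol does not say so, and the same section uses pre-irradiation for the grading at every removal. None of this removes the disagreement between Protocol 3.4 and the analysis sections, or the mixing of reading types in the maximum.

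**Conclusion.** The point holds in a limited form. Protocol 3.4 gives a single attribution to readings that are confounded by earlier UVA: 5 of 6 pre-UVA Induction readings on the default path, and 4 of 6 for a subject moved once who then continues. This assumes the scheduled visits are kept and irradiation is given at each removal unless the relocation rule applies.

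The practical exposure is late-onset reactions after Tuesday irradiations and reactions that recur on re-application, mostly at low grade. How many would occur cannot be estimated from the documents. The study is descriptive with no formal inference, so no error rate or power figure changes.

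Separately, the Protocol 3.4 rule and the planned analysis do not match, and the Induction maximum combines three kinds of reading while leaving out the last post-UVA one. These passages must be reconciled. The point is worth correcting before unblinding, but it does not threaten the Challenge comparison.

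**What to change.** - **Flag.** Add a reading type to the SAP score tables: UVA-naïve; pre-UVA on a previously irradiated site; post-UVA. Assign it by subject and site, so that a relocated site starts again as UVA-naïve. Keep the baseline gradings before patching (Visits 2 and 15) outside the maxima.
- **Maxima.** Replace the pooled phase maximum with one maximum per reading type, and count Visit 14 among the post-UVA Induction readings.
- **Primary irritation.** Treat as pure primary-irritation data only readings of skin that has had no UVA: Visit 3, the first grading at a relocated naïve site, the Visit 16 grading before UVA, and the non-irradiated Challenge site.
- **Mixed readings.** Report the other pre-UVA readings at Visits 5 to 13 separately, next to the preceding post-UVA score, without assigning them solely to irritation or solely to photo-reaction.
- **Wording.** Align Protocol 3.4, 9.2.3 and 9.3.2 and SAP 2.4.1.1 with this scheme, and record the change in SAP section 3.

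The cost is some wording, a derived flag and a few extra table rows. No new visits or data are needed. The mixed readings will not settle either question by themselves, which is a fair statement of what the Induction design can show.
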